12.12.5. Statistical Analysis

The primary sub-study estimand is to compare the treatment effect on change from baseline in 24 hour average SBP at end of sub-study, in all randomized sub-study subjects. The statistical model for analysis will be an ANCOVA with terms for treatment and baseline 24 hour average SBP. This model will provide a point estimate and two-sided 95% CI for the treatment effect and a one-sided p-value for the superiority assessment. Superiority will be established if the p-value is <0.025 . The primary analysis population will be the ABPM sub-study-ITT population defined as randomized subjects who were also entered into the ABPM sub-study.

Given the nature of ABPM measurement, a high degree of dropout unrelated to randomized treatment is anticipated. The potential high level of missing data poses a challenge in the interpretation of the primary ABPM sub-study analysis. The reason for missing ABPM data will be examined to explore the impact of missing data on the sub-study primary efficacy conclusions. If the majority (defined as $>70\%$) of the missing data is due to either subject unwillingness to repeat the ABPM procedure or due to an un-evaluatable reading, then data will be treated as missing at random and the primary analysis

will be considered sufficient. Otherwise, a sensitivity analysis may be performed that will use multiple imputation from the active control arm to replace data from both treatment groups that was missing due to reasons other than subject unwillingness or un-evaluatable readings. Further supplementary analyses may include an ABPM per-protocol population (PP) analysis, utilizing all ABPM-ITT subjects who are not major protocol violators or who did not change BP medications during the sub-study. Further details of sensitivity and supplementary analyses will be described in the RAP.

In order to contextualise the primary between-group comparison, a key secondary objective is to assess within-group changes from baseline over the sub-study. Assessment of within-group changes will support interpretation of the primary analysis by identifying whether there was an absence of an increase in BP in one or both treatment groups. To that end, two-sided 95% confidence intervals will be calculated for change from baseline in each ABPM parameter separately for each treatment group. For either treatment group, a lack of adverse effect on the primary endpoint of average SBP at end of sub-study will be concluded if the upper 95% confidence limit is no more than 4 mmHg. This margin was chosen as it is less than the clinically meaningful change of 5 mmHg [Whelton, 2002] and it is half the historical increase in SBP observed with rhEPO [Krapf, 2009].

The mean and two-sided 95% CI will be estimated from the primary statistical model for within treatment arm SBP change from baseline to end of sub-study.

The change from baseline 24 hour average DBP, mean arterial pressure and heart rate at end of sub-study will be assessed in a similar way as the primary, using analogous ANCOVA models with treatment and baseline as covariates.

The differences in proportion of subjects that increase/decrease their BP medication (number or dose) will be assessed using Fisher's Exact Test. The differences between treatment groups in the proportion of subjects that convert from dippers/non-dippers at baseline to non-dippers/dippers at end of sub-study will also be assessed using Fisher's Exact Test.

Plots of the mean 24 hour average values (two-sided 95% CIs) and mean changes from baseline in 24 hour average values (two-sided 95% CIs) for BP will be provided by treatment group.

Additional statistical considerations will be addressed in the RAP.

References

Agarwal R. Blood Pressure and Mortality Among Hemodialysis Patients. *Hypertension*. 2010; 55:762-768.

Peixoto AJ ,Santos SF, Mendes RB, Crowley ST, Maldonado R , Orias M, et al. Reproducibility of ambulatory blood pressure monitoring in hemodialysis patients. *Am J Kidney Dis*. 2000; 36: 983–990.

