4. STUDY DESIGN

4.1. Overall Design

- This is a randomized, open-label (sponsor blind), active-controlled, parallel-group, multi-center, event-driven study in dialysis subjects with anemia associated with CKD who are currently treated with ESAs².

[figure not shown]
² ESAs refer to any rhEPO or methoxy PEG-epoetin beta.

- This study will comprise four study periods (Figure 1): a 4-week screening period, a 4-week placebo run-in period, a treatment period and a follow-up period. Prior ESA therapy continues during the screening and run-in periods.
- The treatment period consists of :
 1. The stabilization period, defined as the period from Day 1 to Week 28 during which randomized treatment will be dose titrated to achieve the appropriate Hgb target
 2. The maintenance period, defined as the period from the end of the stabilization period (Week 28) to the end of treatment (variable per subject), to assess long term safety and efficacy.
 - The efficacy evaluation period (EP) is defined as the period from Week 28 to Week 52 during which Hgb efficacy will primarily be assessed.
- The total duration of the study is dependent upon the accumulation of 664 adjudicated first MACE (i.e., it is event-driven) unless review of interim data by the IDMC recommends bringing the study to an earlier close.
- All subjects will remain in the study (including subjects receiving kidney transplant), regardless of whether they continue with randomized treatment (unless consent for any further follow up is withdrawn), until the target number of first adjudicated MACE has occurred. At that point, the sponsor will notify investigators to have subjects come in for an End of Study visit within a pre-defined time period.
- The end of the study will occur after the accumulation of 664 adjudicated first MACE and the last subject has completed their last required study visit (Section 7.1).
- Subjects will be stratified by dialysis type [HD* or PD], by region (see Appendix 3), and by participation in the ABPM sub-study. Dialysis type and region are stratification factors considered to be potentially prognostically important, i.e., predictive of study endpoints while participation in the ABPM sub-study is an administrative stratification factor intended solely to ensure a similar number of sub-study subjects in each of the two randomized groups.

* HD group also includes hemodiafiltration (HDF) or hemofiltration (HF).

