9.4. Key Elements of Analysis Plan

9.4.1. Primary Analyses

9.4.1.1. Primary CV Safety Analysis (co-primary)

MACE: The co-primary cardiovascular safety analysis is to assess the comparative treatment effect for time to first occurrence of adjudicated MACE in all randomized subjects. Time to the first occurrence of a primary endpoint event will be computed as (event date – randomization date) +1. Subjects who do not have the event during the trial period will be censored in the analysis, with details provided in the RAP. The statistical model is a Cox Proportional Hazards regression model, adjusting for treatment and the prognostic randomization stratification factors (dialysis type and region), to estimate the hazard ratio, two-sided 95% CI and one-sided p-value for the statistical non-inferiority test. Non-inferiority will be established if the upper limit of the two-sided 95% CI is less than the margin of 1.25. Cumulative time from randomization to first event or end of trial will be evaluated using Kaplan-Meier methodology and displayed graphically. Treatment comparisons from the Cox regression model will be presented as hazard ratios and two-sided 95% CIs and displayed on forest plots. The validity of the proportional hazards assumption will be assessed. All adjudicated events will be used for the primary analysis and concordance between investigator reported and adjudicated events will be summarized.

Sensitivity and Supportive Analyses: A sensitivity analysis will be performed to address potential effects of drop outs and to evaluate the robustness of the co-primary

MACE analysis. A sensitivity “tipping point” analysis utilizing multiple imputation for randomized subjects who have withdrawn from the study will be performed, as well as a supportive “on-drug” analysis to evaluate the comparative treatment effect during the time that subjects remain on randomized treatment (plus a window of 28 days). Full details will be provided in the RAP.

In addition, analyses will be performed for each component of MACE (all-cause mortality, MI and stroke) to understand individual contributions to the overall MACE result and to assess component directional consistency. These analyses will not be multiplicity adjusted. Further subgroup and covariate adjusted analyses of specific clinical interest are detailed in Section 9.4.4 and the RAP.

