9.4.1.2. Primary Efficacy Analysis (co-primary)

Mean change in Hgb between baseline and the EP (Weeks 28 to 52): The primary efficacy estimand is the effect of daprodustat relative to rhEPO on the change in Hgb from baseline to the average of all values in the EP, regardless of adherence to treatment including interruptions and discontinuation, the use of non-randomized ESA medication for any reason including rescue therapy, or the use of blood transfusions, in subjects on dialysis currently treated with an ESA with anemia secondary to CKD and assuming subjects do not die before the end of the EP. The analysis will use an ANCOVA model. For each subject, baseline Hgb will be the value obtained on Day 1, prior to taking randomized treatment, and Hgb during EP will be determined by calculating the mean of all available and imputed Hgb values between Weeks 28 to 52 inclusive regardless of adherence to randomized treatment. The ANCOVA model will include prognostic randomization stratification factors (dialysis type and region), baseline hemoglobin and treatment. It will provide a point estimate and two-sided 95% CI for the treatment effect together with the one-sided non-inferiority test p-value. Non-inferiority will be established if the lower limit of the two-sided 95% CI is greater than the margin of -0.75 g/dL. Imputation will be used for missing Hgb data; further details will be provided in the RAP.

Sensitivity and Supportive Analyses: Sensitivity analyses for the primary estimand will include a multiple imputation-based “tipping point” analysis where assumptions are adjusted until non-inferiority is lost by imputing data for subjects who did not fully complete the EP. A supportive analysis will evaluate efficacy in those subjects who adhere to randomized treatment, defined as ITT subjects with at least one on-treatment Hgb during the EP (this approach corresponds to evaluating an efficacy estimand). A supportive “tipping point” analysis as that described above for the primary analysis will be performed for this “on-drug” analysis. In addition, a per-protocol supportive analysis will estimate the treatment effect in subjects who strongly adhere to the protocol, and supportive analyses to explore a shorter EP (Weeks 28 to 36) will be performed for the co-primary effectiveness estimand and “on-drug” efficacy estimand. Full details of all sensitivity and supportive analyses will be provided in the RAP.

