9.4.2. Secondary Analyses

9.4.2.1. Principal Secondary Analyses

Conditional on the co-primary endpoints achieving at least non-inferiority at the one-sided 2.5% level, statistical testing will progress to superiority for MACE and the principal secondary endpoints. The hypotheses to be tested for these endpoints are as follows:

- **Null:** daprodustat is not superior to rhEPO (i.e. the hazard ratio is greater than or equal to 1.0 for time-to-event endpoints, or the mean difference is greater than or equal to 0 for continuous endpoints)
- **Alternative:** daprodustat is superior to rhEPO (i.e. the hazard ratio is less than 1.0 for time-to-event endpoints, or the mean difference is less than to 0 for continuous endpoints)

These tests will be multiplicity adjusted based on a family-wise Type I error rate set at the one-sided 2.5% level, see Section 9.4.3 for further details.

For “time to event” endpoints: The statistical modeling approach described for MACE in Section 9.4.1.1 will be repeated for the adjudicated composite endpoints of:

- MACE or a thromboembolic event (vascular access thrombosis, symptomatic deep vein thrombosis or symptomatic pulmonary embolism).
- MACE or hospitalization for HF.

For the average monthly IV iron dose up to Week 52 endpoint: IV iron use for all subjects will be recorded in the eCRF and the average monthly IV iron dose up to week 52 will be calculated. An ANCOVA model will be used to compare the difference in this average monthly IV iron dose per subject between arms, including factors for baseline dose, treatment and the prognostic randomization stratification factors.

Additional secondary endpoints are listed in [Appendix 2](#). All analyses of secondary endpoints are of exploratory nature, summary statistics and nominal one-sided p-values will be used for any treatment comparisons.

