12.12.3.2. Eligibility Criteria – Screening

Additional Inclusion Criteria

In addition to meeting entry criteria for the main study, a subject will be eligible for inclusion in this sub-study only if all of the following criteria apply.

1. Signed written informed consent prior to beginning sub-study-related procedures.
Note: Consent to participate in this sub-study is separate from consent to participate in the main study, and will be signed either at Week -8 or at Week -4 prior to ABPM assessments.
2. Use of the same antihypertensive treatment for the 6 weeks prior to the Screening visit, through the entire Screening period and at randomization.
3. SBP of ≤ 170 mmHg based on the average of pre-dialysis clinic values obtained at Week -8 and Week -4 using the methodology described in the SRM.
4. Willing and able to wear ABPM device for 24 hours on two separate sessions.
5. Valid ABPM at baseline [**randomization (Day 1) only**].
6. Dialysis schedule of three times per week.
7. Average awake-time SBP of ≤ 150 mmHg as assessed by a valid baseline ABPM [**randomization (Day 1) only**].

Additional Exclusion Criteria

A subject will not be eligible for inclusion in this sub-study if any of the following criteria apply:

1. Receiving peritoneal dialysis or home HD.
2. Subjects who are at high risk for loss to follow-up (e.g., subjects who are known to not regularly attend dialysis, subjects who may require frequent hospitalizations or vascular access interventions).
3. Evidence of atrial fibrillation or atrial flutter at time of baseline ABPM assessment (see Section 12.12.3.3).
4. Oscillometer/sphygmomanometer cuff cannot accommodate their upper arm circumference.
5. BP cannot be measured in the arm opposite of current vascular access.
6. Subjects who experience, on average, >5% increase in weight above EDW between mid-week dialysis treatments between Week -8 and baseline ABPM reading.

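### The ABPM sub-study ANCOVAs leave out region, a factor its subjects were randomized by and the protocol calls potentially prognostic; adding it is a near-free gain in precision

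*Protocol*

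**What the plan says.** Section 4.1 sets out the randomization: "Subjects will be stratified by dialysis type [HD* or PD], by region (see Appendix 3), and by participation in the ABPM sub-study". It then separates the factors by purpose: "Dialysis type and region are stratification factors considered to be potentially prognostically important, i.e., predictive of study endpoints", whereas sub-study participation is described as purely administrative. A subject who enters the ABPM sub-study is therefore allocated within region.

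Section 12.12.3.2 lists among the sub-study exclusions "Receiving peritoneal dialysis or home HD". With PD excluded, dialysis type as stratified (HD or PD) is constant in the sub-study, and region is the only prognostic stratification factor that still varies.

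Section 12.12.5 gives the primary model: "The statistical model for analysis will be an ANCOVA with terms for treatment and baseline 24 hour average SBP". Diastolic pressure, mean arterial pressure and heart rate are to be analysed "using analogous ANCOVA models with treatment and baseline as covariates". The section gives no reason for leaving region out.

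The main-trial models that the protocol writes out do carry region:
- Section 9.4.1.1 includes dialysis type and region in the Cox model for MACE, and 9.4.2.1 repeats that approach for the composites.
- Section 9.4.1.2 says of the Hgb analysis: "The ANCOVA model will include prognostic randomization stratification factors (dialysis type and region), baseline hemoglobin and treatment".
- Section 9.4.2.1 describes the IV iron ANCOVA as "including factors for baseline dose, treatment and the prognostic randomization stratification factors".
- Section 9.4.4 carries the original covariates into the subgroup models.

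**The concern.** Stratifying by region balances it between the arms, so any between-region variation in SBP change contributes little to the true variance of the treatment difference. A model without region still counts that variation as residual error. The estimate stays unbiased, but its standard error is then too large, the interval too wide and the one-sided p-value too high on average.

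The sub-study has a formal superiority test at one-sided 0.025 and is planned at slightly over 80% power, so precision is not in surplus. Section 12.12.5 also takes the within-arm SBP intervals from this same model and judges their upper limits against 4 mmHg, so the residual variance enters a second decision rule.

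This is not a detail left to the analysis plan. The protocol states the covariate list, and 12.12.5 defers only the sensitivity and supplementary analyses and additional considerations.

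**Working it through.** **Inputs from Section 12.12.4:** one-sided alpha 0.025; SD of SBP change 11 mmHg; difference 6 mmHg in favour of daprodustat; 68 per group; up to 20% withdrawal. Allocation is 1:1 (Section 4.1). Appendix 3 has 5 regions.

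**Reproducing the stated figures**
- Evaluable per arm: 68 × 0.8 = 54.4, taken as 54.
- SE of the difference: 11 × √(2/54) = 2.117 mmHg.
- Noncentrality: 6 / 2.117 = 2.834.
- Power: 80.2% (noncentral t, 106 df), or 80.9% by the normal approximation. The protocol says greater than 80%.
- Smallest significant difference: 4.20 mmHg by t. The protocol says 4.2.
- Required n by t: 54 per arm; 54 / 0.8 = 67.5, rounded up to 68, as stated.

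**Adding region.** Let R² be the share of residual variance explained by region. The documents give no value, so it is assumed over a range. No credit is taken for variance removed by baseline.

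*Region in the model:* residual SD = 11 × √(1 − R²); residual df = 108 − 2 − 1 − 4 = 101. At R² = 5% the SE is 2.117 × √0.95 = 2.063 and the noncentrality 6 / 2.063 = 2.908. At R² = 10% the SE is 2.117 × √0.90 = 2.008 and the noncentrality 6 / 2.008 = 2.988.

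*Region omitted:* the true SE also falls to 2.063 or 2.008 because stratification balances region, but the model still estimates about 2.117 (105 df). The critical difference therefore stays at about 4.20. Approximate power at R² = 5% is Φ((6 − 4.20) / 2.063) = Φ(0.87), about 80.8%. The table's figures for this model come from 2,000,000 simulated draws per R², assuming region is balanced between arms.

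| Assumed R² | Power with region | Power without | CI half-width with region (mmHg) | CI half-width without (mmHg) | One-sided type I error without |
|---|---|---|---|---|---|
| 0 | 80.2% | 80.2% | 4.20 | 4.20 | 2.5% |
| 2% | 80.9% | 80.5% | 4.16 | 4.20 | 2.4% |
| 5% | 82.1% | 80.8% | 4.09 | 4.20 | 2.2% |
| 10% | 84.1% | 81.5% | 3.98 | 4.20 | 1.9–2.0% |

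The gain in power from adding region is 82.1 − 80.8 = 1.3 points at 5% and 84.1 − 81.5 = 2.6 points at 10%. If region explains nothing, the 4 degrees of freedom move the half-width only from 4.198 to 4.199 mmHg.

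**The case against.** The strongest reply is that nothing here is invalid. Under stratified 1:1 randomization, an ANCOVA on treatment and baseline is unbiased, its type I error is at or below 2.5%, and every stated sample-size figure reproduces. No passage promises that the sub-study model will carry the stratification factors. All of this stands: the point concerns efficiency and consistency, not error control.

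The second reply is that the benefit rests on an assumed R². Section 4.1 speaks of study endpoints in general, not of 24-hour SBP change. The sub-study also limits regional variation. It requires stable antihypertensives up to randomization, three-times-weekly dialysis and an awake SBP ceiling, and it prefers no change in dry weight or antihypertensives. This stands as a limit on size; a small R² is quite possible.

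A reader might infer three stronger things that the documents do not support:
- **That adding region lifts power from 80.2% to 82% or 84%.** The 80.2% figure belongs to R² = 0. When region is prognostic, the model without it also gains power, to 80.8% and 81.5%, so the difference is smaller.
- **That the sub-study has only 80% power.** The protocol says greater than 80% with up to 20% withdrawal. With no withdrawals the same inputs give 88.4% by t.
- **That every main-trial analysis adjusts for region.** This holds for the models written out in the protocol. The main-study blood pressure endpoints and patient-reported outcomes have no model specified there.

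Finally, some regions may have few subjects, because only selected countries take part. That calls for a pooling rule but is no reason to drop the factor.

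**Conclusion.** The point holds as a minor one. The ABPM models omit the one prognostic stratification factor that still varies among sub-study subjects. This departs, without explanation, from the convention of the main-trial models the protocol specifies. The planned analysis remains valid and somewhat conservative, and the sample size and stated power are not wrong.

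The size depends wholly on how much of the variance in SBP change region explains. The loss is nil at R² = 0, 0.4 points of power at 2%, and the 1.3 and 2.6 points shown above at 5% and 10%. These figures assume 54 evaluable subjects per arm, SD 11 mmHg, five regions and balance of region between arms. Since adding region costs almost nothing if it is not prognostic and helps if it is, including it is the better choice.

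**What to change.** Before unblinding, amend Section 12.12.5 so that the primary analysis is an ANCOVA with terms for treatment, baseline 24-hour average SBP and region as randomized. Use the same structure, with the corresponding baseline, for DBP, MAP and heart rate. Regions with very few sub-study subjects should be pooled, with the pooling rule set blind to treatment. Dialysis type need not be added. If the sponsor prefers to keep region out, the section should say why.

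The cost is one model term and at most 4 of about 105 residual degrees of freedom, fewer if the participating countries cover fewer than five regions. The sample size and the stated power need no change.

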12.12.2. Objectives and Endpoints

Objectives	Endpoints
Primary	

 To compare daprodustat to rhEPO for effect on SBP (superiority) by ABPM in subjects receiving maintenance hemodialysis in the ABPM ITT population 	
 Change in 24 hour average SBP from baseline to end of sub-study¹ between treatment groups
Secondary	

 To assess the effect of daprodustat and rhEPO independently within treatment group on SBP, DBP and mean arterial blood pressure (MAP) by ABPM in the ABPM ITT population 	
 Change in 24 hour average SBP from baseline to end of sub-study¹ within each treatment group Change in 24 hour average DBP from baseline to end of sub-study¹ within each treatment group Change in 24 hour average MAP from baseline to end of sub-study¹ within each treatment group

 To compare the effect of daprodustat to rhEPO on DBP and MAP by ABPM in the ABPM ITT population 	
 Change in 24 hour average DBP from baseline to end of sub-study¹ between treatment groups Change in 24 hour average MAP from baseline to end of sub-study¹ between treatment groups

 To compare the effect of daprodustat to rhEPO on BP parameters in the ABPM per-protocol population 	
 Change in: 
 24 hour average SBP 24 hour average DBP 24 hour average mean arterial pressure from baseline to end of sub-study¹ between treatment groups

Objectives	Endpoints

 To assess the effect of daprodustat and rhEPO on BP parameters in the ABPM per-protocol population 	
 Change in: 
 24 hour average SBP 24 hour average DBP 24 hour average mean arterial pressure from baseline to end of sub-study¹ within each treatment group

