12.12.3.5. Estimated Dry Weight and Antihypertensive Medication Changes

It is preferred that no changes are made to EDW and antihypertensive medications while the subject is part of the sub-study.

If changes in EDW and/or antihypertensive medications are necessary, these must be documented in the eCRF along with the reasons. Subjects will remain in the sub-study regardless of any changes.

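### The ABPM per-protocol population is defined with 'or' where 'and' is needed, so read literally it drops only subjects who are both major violators and BP-medication changers (minor)

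*Protocol*

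**What the plan says.** Section 12.12.5 makes the ABPM-ITT population primary, "defined as randomized subjects who were also entered into the ABPM sub-study". It then adds: "Further supplementary analyses may include an ABPM per-protocol population (PP) analysis", with that set "utilizing all ABPM-ITT subjects who are not major protocol violators or who did not change BP medications during the sub-study". The next sentence refers the reader onward: "Further details of sensitivity and supplementary analyses will be described in the RAP".

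Section 12.12.2 gives this population a larger role. Two secondary objectives are set in it alone: "To compare the effect of daprodustat to rhEPO on BP parameters in the ABPM per-protocol population" and "To assess the effect of daprodustat and rhEPO on BP parameters in the ABPM per-protocol population". Three more, on the dipping pattern and on conversion between dipper and non-dipper status in each direction, are set in both the ABPM-ITT and the per-protocol populations. That makes five in all.

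Section 12.12.3.5 covers medication changes during the sub-study: "It is preferred that no changes are made to EDW and antihypertensive medications while the subject is part of the sub-study". Where a change is needed it is recorded with its reason, and "Subjects will remain in the sub-study regardless of any changes".

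**The concern.** The definition is an inclusion rule with two alternatives joined by 'or'. A non-violator whose antihypertensives were changed meets the first alternative and stays in. A major violator whose antihypertensives were not changed meets the second and also stays in. A per-protocol set that admits major violators because their BP medication was stable does not do what its name says.

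At stake is the check that such a set would naturally provide. Treatment is open-label to investigators (Section 6.4), and they may adjust antihypertensives during the sub-study. An adjustment can mask a rise in blood pressure. A set without such adjustments would show whether the ABPM-ITT picture depends on them, and the written rule does not deliver that set.

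**Working it through.** **1. The plan's own figures.** Section 12.12.4 gives no size for the per-protocol set. It does give the sub-study sample size: 68 per group, SD 11 mmHg, difference 6 mmHg, one-sided 2.5%, up to 20% withdrawal, more than 80% power.
- n per arm = 2 × (1.960 + 0.842)² × 11² / 6² ≈ 53. Then 53 / 0.8 gives 67, against 68 stated.
- 68 × 0.8 ≈ 54 evaluable per arm gives power of 80.9% (normal) or 80.2% (t).
- The smallest significant difference is 4.20 mmHg, as stated.

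The stated figures reproduce, and the fault lies only in the set definition.

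**2. Set logic.** Let v be the share of major violators and c the share who changed BP medication.
- 'Or' excludes only the overlap: v × c if independent, and at most min(v, c). It keeps 1 − vc under independence.
- 'And' excludes anyone in either group. It keeps (1 − v)(1 − c) under independence.

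**3. Inputs.** The documents do not give v, so 10% is assumed. For c the nearest figures are the antihypertensive increases in haemodialysis subjects in Appendix 4:
- 24-week phase 2b: 22/177 (12%) daprodustat, 2/39 (5%) control.
- 52-week Japan phase 3: 51/136 (38%) daprodustat, 66/135 (49%) rhEPO.

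**4. Results at v = 10%, independence, 136 subjects.**

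| c | 'or' keeps | 'and' keeps |
|---|---|---|
| 5% | 1 − 0.005 = 99.5% (135) | 0.90 × 0.95 = 85.5% (116) |
| 12% | 1 − 0.012 = 98.8% (134) | 0.90 × 0.88 = 79.2% (108) |
| 38% | 1 − 0.038 = 96.2% (131) | 0.90 × 0.62 = 55.8% (76) |
| 49% | 1 − 0.049 = 95.1% (129) | 0.90 × 0.51 = 45.9% (62) |

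Under independence 'or' keeps a share 1 − v of the changers, which is 90% here.

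**5. Sensitivity.** Over v = 5-30% and c = 5-49%, still independent, 'or' keeps 116 to 136 of the 136 and 'and' keeps 49 to 123. If the two groups overlap as much as possible, the gap narrows to |v − c|. At v = 10% and c = 12%, 'or' then keeps 90% and 'and' 88%; at c = 38% they keep 90% and 62%. Near-complete overlap would be expected if a medication change counted as a major violation, but Section 12.12.3.5 states only a preference against changes.

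**The case against.** The strongest reply is that this is a drafting slip whose operative definition belongs elsewhere. Section 9.3.1 allows sub-study populations to be defined in the RAP, Section 12.12.5 says only that the per-protocol analysis may be done, and a sensible reader would guess that 'and' was meant. The RAP may already say so. This lowers the stakes. It does not make the protocol text right: the protocol did not leave the definition open, no other section gives a different one, and a RAP using 'and' would contradict it.

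Two further points stand in full. Every SBP, DBP and MAP comparison in the per-protocol set sits beside the same comparison in ABPM-ITT, and medication changes are compared between arms in their own right. Also, the protocol never states that the per-protocol set is meant to isolate a BP effect free of medication changes; that purpose is inferred from the clause.

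The documented rates fit poorly too. They count increases only and come from other studies of 24 or 52 weeks. This sub-study is in in-center haemodialysis subjects and ends at Week 16 (Week 28 for early completers). The 52-week rates are therefore best read as an upper illustration. Only the 38% there is a daprodustat figure; 49% is rhEPO.

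**Conclusion.** The definition is wrong as written, and the consequence is minor. The literal set is close to ABPM-ITT: about 99% of subjects are kept at the nearest proxy rates, against about 79-86% under 'and'; at the 52-week rates it is about 95-96% against 46-56%. These sizes rest on an assumed 10% violator rate, on independence of violation and change, and on proxy change rates. That 'or' gives the larger set does not depend on them; the size of the gap does.

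A reader might infer that the per-protocol results would simply repeat the ITT results. The documents do not support that: the sets are near-identical, not identical, and with strong overlap 'or' could remove up to the smaller of v and c. A reader might also infer that the sub-study's main conclusion is at risk. It is not: superiority is tested in ABPM-ITT, the within-group SBP interval judged against 4 mmHg comes from the primary model, and the sample size reproduces.

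**What to change.** In Section 12.12.5, replace 'or' with 'and', so that a subject must be free of major protocol violations and also have had no BP-medication change during the sub-study. Use the same definition in the RAP, and report the number excluded for each reason by arm.

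The edit is one word in the protocol plus the RAP definition, and conduct does not change. The price is a smaller and less precise set: about 108 to 116 of 136 at the 24-week rates and 62 to 76 at the 52-week rates, under the assumptions above. The corrected set also conditions on a medication change made after randomization in an open-label trial, possibly in response to blood pressure itself, so a difference between arms within it is not clean evidence of a treatment effect. Present it as supportive only.
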